5.6.1 Baseline Data

Baseline and demographic characteristics will be summarized by standard descriptive summaries (e.g. means and standard deviations for continuous variables such as age).

5.6.2 Efficacy Analysis

Our principal hypotheses relate to baseline to STX administration changes in the latency of the auditory M50, M100 and MMF responses, and gamma-band total power and inter-trial coherence (examined pre- and post-stimulus). To this end, for each dependent measure, ANOVAs with dose as a repeated measure will examine baseline versus post acute-dose changes (analyses showing no significant differences across time in baseline M50, M100, MMF and gamma measures will allow use of a single averaged baseline measure). Contrasts of *a priori* interest assess (1) a baseline versus post-acute dose change in the dependent measures averaging across STX209 15 and 30 mg, as well as (2) a change in dependent measures from baseline versus STX209 15 mg versus STX209 30 mg, with this test demonstrating an effect of dose. For the secondary endpoints, associations between MRS GABA/Cr ratios and the MEG dependent measures will be assessed using Pearson correlation analyses.

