2.1 Primary Objective (or Aim)

1. To determine whether STX209 produces a significant change in MEG target parameters compared to baseline as well as compared to placebo treatment. Secondly, to determine if the magnitude of such change is influenced by STX209 dose: 0mg (placebo) versus 15mg versus 30mg.
2. To determine whether STX209 leads to a significant change in MRS-obtained auditory cortex GABA levels compared with placebo treatment. Secondly, to determine whether the magnitude of the GABA change is influenced by STX209 dose level.
3. To determine if dose-dependent changes in MEG target parameters are correlated to dose-dependent changes in MRS target parameters in auditory cortex.

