4.3 MEG and MRI/MRS Assessment Phase: Visit 1-3

On the next three visits (scheduled to occur within 3 months of the physical examination and within 12 months of clinical/behavioral testing) MEG, MRI and MRS measures will be collected at each study visit. Upon arrival, vital signs will be collected. Then pre-drug MEG data will be collected to obtain baseline measures. At the conclusion of the baseline MEG scan, participants will be randomly administered a single-dose of Placebo and single-dose of STX209 in order of smallest to largest dose (15mg, 30mg) (see Section 3.2). Based on advice from Clinical Research Associates, LLC (CRA), given the time course of plasma STX209 levels, the MEG examination will be repeated 60 minutes after drug administration. Following the MEG exam, subjects will obtain a 3T MRI to obtain an anatomic 3D image (MP-RAGE) and bilateral STG GABA and glutamate measures (MEGAPRESS MRS). At the end of the scanning visit AE will be assessed via the SMURF form. Subjects will return for their imaging visit no less than four days or more than 14 days to repeat the MEG, MRI and MRS exams, each time with a different drug/placebo dose.

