5.5 Secondary Endpoints

Secondary endpoints will include the following:

- The change from baseline to STX209 administration in left and right superior temporal gyrus GABA levels.
- Safety and tolerability of STX209 based on Adverse Events. Measurements and evaluations

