5.6 Statistical Methods

Primary statistical analyses assess baseline versus post acute-dose (placebo, STX209 15 and 30 mg) changes for (1) M100 auditory latency, and (2) post-stimulus auditory gamma-band activity. For each dependent measure, ANOVAs with dose as a repeated measure will examine baseline versus post acute-dose changes (analyses showing no significant differences across time in baseline M100 and gamma measures will allow use of a single averaged baseline measure). Contrasts of *a priori* interest assess (1) a baseline versus post-acute dose change in the dependent measures averaging across STX209 15 and 30 mg, as well as (2) a change in dependent measures from baseline versus STX209 15 mg versus STX209 30 mg, with this test demonstrating an effect of dose. Secondary and exploratory analyses examine baseline to post acute-dose response changes in MRS auditory GABA concentration as well as associations between MEG functional measures and MRS GABA concentration.

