6.1.3 Dosing

This is a study examining the acute effect of STX209 on brain activity at two different doses: 15mg and 30 mg. Subjects will receive STX209 via oral disintegrating tablets, administered in individual 15 mg tablets. Over a period of three visits, participants will randomly receive a single-dose of Placebo and in order of smallest to largest a single-dose of STX209 (15mg, and 30mg).

Dosage	Tablets Administered
15mg	One 15mg tablets STX209 and one placebo
30mg	Two 15mg tablets STX209 and no placebo
Placebo	Zero STX209 tablets and two placebo

Across the three visits, all subjects will receive all doses, with the subject and the study investigators blind to dose until the close of the study.

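### Aim 3 asks whether changes in MEG and GABA are correlated, but the only analysis named correlates their levels

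*Combined protocol and SAP*

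**What the plan says.** Section 2.1 gives the third aim as "To determine if dose-dependent changes in MEG target parameters are correlated to dose-dependent changes in MRS target parameters in auditory cortex". The synopsis repeats it. Section 6.1.3 makes clear that the dose comparison is within subject: "Across the three visits, all subjects will receive all doses". Section 4.3 adds that "MEG, MRI and MRS measures will be collected at each study visit", so each subject can supply up to three MEG–MRS pairs.

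The analysis is stated twice. Section 5.6.2 says that the associations of GABA/Cr ratios with the MEG dependent measures "will be assessed using Pearson correlation analyses". Section 5.6, like the synopsis, lists among the secondary and exploratory analyses "associations between MEG functional measures and MRS GABA concentration". Neither place says that changes are correlated, which dose or visit supplies the pair, or how several pairs from one subject are handled.

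The GABA secondary endpoint in Section 5.5 is worded as a change: "The change from baseline to STX209 administration in left and right superior temporal gyrus GABA levels". On timing, Section 4.3 states "Following the MEG exam, subjects will obtain a 3T MRI", which puts MRS after the post-dose MEG. The visit tables in Section 5.2.1 split the MRI session around dosing and do not say in which part the MRS is acquired.

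**The concern.** The aim is about change and the stated method is about level. Section 5.6.2 draws this distinction itself: its contrasts are described as changes in the dependent measures, while the correlation sentence refers to the measures alone. An analyst who follows the text would correlate GABA/Cr with, say, M100 latency at some visit.

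Such a correlation mixes two things: whether subjects with high GABA tend to have fast responses whatever they were given, and whether a subject's response moves when GABA moves under drug. Only the second bears on Aim 3. The mixture can mislead both ways: a stable trait association may be taken as evidence about the drug, or a real association of changes may be diluted and missed.

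**Working it through.** The documents give no correlation, power or sample size for Aim 3, so there is no planned figure to reproduce.

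**Inputs.** N = 36 and alpha 0.05 (Section 5.7; two-sided assumed); three visits per subject (Section 4.3). The intraclass correlation ρ of each measure and the correlations are not in the documents. I assume ρ = 0.3, 0.5 and 0.7, equal for both measures, and correlations of 0 or 0.4.

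**Model.** Each measure is √ρ·B + √(1−ρ)·W, with B a stable subject level and W a visit-specific part. Let r_B and r_W be the MEG–GABA correlations of the two parts.
- Correlation of levels at one visit: ρ·r_B + (1−ρ)·r_W.
- Correlation of within-subject differences: B cancels, leaving r_W, the Aim 3 quantity.
- Probability of significance (Fisher z): Φ(z√33 − 1.96) + Φ(−z√33 − 1.96), with z = atanh(r), √(N−3) = √33 = 5.745.

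**Case A: only stable levels correlate (r_B = 0.4, r_W = 0).**

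| ρ | level r | z√33 | Fisher | simulated (20,000 runs) | change score, simulated |
|---|---|---|---|---|---|
| 0.3 | 0.3 × 0.4 = 0.12 | 0.693 | 10.7% | 10.8% | 5.1% |
| 0.5 | 0.5 × 0.4 = 0.20 | 1.165 | 21.4% | 21.7% | 4.8% |
| 0.7 | 0.7 × 0.4 = 0.28 | 1.653 | 37.9% | 38.3% | 4.9% |

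**Case B: only changes correlate (r_B = 0, r_W = 0.4).**

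| ρ | level r | Fisher | simulated | change score, simulated |
|---|---|---|---|---|
| 0.3 | 0.7 × 0.4 = 0.28 | 37.9% | 38.8% | 69.7% |
| 0.5 | 0.5 × 0.4 = 0.20 | 21.4% | 21.5% | 69.2% |
| 0.7 | 0.3 × 0.4 = 0.12 | 10.7% | 10.6% | 69.4% |

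For the change score, Fisher gives z√33 = 0.4236 × 5.745 = 2.434, hence 68.2%.

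**Conditional case: three visits pooled as 36 × 3 = 108 independent pairs, no association at any level.** The variance of r grows by about 1 + 2ρ² = 1.18, 1.50 and 1.98. The nominal 5% test then rejects with probability 2Φ(−1.96/√(1 + 2ρ²)) = 7.1%, 11.0% and 16.4%. Simulation with 100,000 runs gives 7.2%, 10.9% and 16.5%.

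**Check on a tempting remedy.** A repeated-measures correlation without a dose term also removes B, but it picks up any mean dose shift common to both measures. With independent visit-specific parts and a linear placebo-to-30 mg shift of 0.5, 0.75 or 1.0 within-subject SD in both measures, it is significant in about 8%, 18% and 40% of trials. With a dose term, or with change scores, it stays at 5%.

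**The case against.** The strongest reply is that the text is incomplete rather than wrong. The correlation sentence opens by referring to the secondary endpoints, and the GABA endpoint in Section 5.5 is a change. Pearson correlation of one change score per subject is valid and would address Aim 3. That stands: the method is not the defect. But the sentence names ratios and measures, and no change score for this correlation is defined anywhere. A change from baseline in GABA also needs a pre-dose MRS value, which Section 4.3 does not describe.

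Correlating levels also has a proper use. The synopsis rationale and Sections 1.2 and 2 set a general goal of relating electrophysiological markers to GABA and glutamate levels, and a correlation of levels suits it. That stands too; it leaves Aim 3 without an analysis explicitly tied to it.

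A reader might infer that the plan treats 108 dependent pairs as independent and so runs at 7% to 17% error. The documents do not support this, because pooling is never stated. A reader might also count 7 MEG measures × 2 hemispheres × 3 visits = 42 tests. That rests on an assumed by-visit analysis, so I give it no weight.

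Finally, Section 5.6 calls this analysis secondary and exploratory, although Section 2.1 lists the aim under the primary objective. This lowers the stakes without removing the mismatch.

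**Conclusion.** The point holds as a mismatch between aim and stated analysis, together with missing specification. Followed literally, Section 5.6.2 does not estimate the Aim 3 quantity. Under the assumptions shown, a single-visit test on levels reports an association in about 11% to 38% of trials when changes are uncorrelated, and finds a true correlation of changes of 0.4 in only about 39% to 11%, against about 69% for change scores. The size depends on the unknown intraclass correlations: stable measures make both errors worse. It does not follow that Pearson correlation is invalid here or that the error rate is inflated; the latter would be true only if visits were pooled. The point is worth correcting before analysis, but it does not threaten the primary MEG comparisons.

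**What to change.** For Aim 3, state in Section 5.6.2 that the Pearson correlation is between each subject's active-minus-placebo change in post-dose GABA/Cr and the matching active-minus-placebo change in the MEG measure, one pair per subject. Say whether 15 and 30 mg are averaged or taken separately. This needs no pre-dose MRS. Sections 4.3, 5.2.1 and 5.5 should still be reconciled on when MRS is acquired and what baseline the GABA endpoint uses.

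Name one lead MEG measure and label the others exploratory. Keep the correlation of levels as a descriptive analysis of the general MEG–GABA relationship.

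If a repeated-measures correlation or a mixed model with subject-centred GABA/Cr is preferred, include dose and visit as factors, so that a mean shift in both measures is not read as an individual-level link.

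A similar caution applies to change scores. Placebo falls at visit 1, 2 or 3, so with the two doses averaged a linear visit drift enters with weight 2.5 − 1 = +1.5, 2 − 2 = 0 or 1.5 − 3 = −1.5 visit steps. Drift in both measures could therefore produce a correlation; a partial correlation given dosage order is a simple check.

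The cost is SAP wording and minor analysis work, with no new data. Subjects without both a placebo and an active visit drop out of this correlation, although Section 6.1.4 keeps their data elsewhere. Precision is modest: with one pair per subject and N = 36, 80% power needs a true correlation of about 0.45.

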5.6.3 Pharmacokinetic Analysis

N/A

5.6.4 Safety Analysis

All subjects entered into the study at screening visit will be included in the safety analysis. The frequencies of AEs by type, body system, severity and relationship to study drug will be summarized. SAEs (if any) will be described in detail.

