Efficacy Evaluations	The measures used to assess efficacy of STX209 will be as follows: 
 1. Change from baseline to STX209 administration in left and right superior temporal gyrus auditory M50, M100 and MMF latencies. 2. Change from baseline to STX209 administration in left and right superior temporal gyrus auditory gamma total power and phase-locking measures (examined pre- and post-stimulus).
Safety Evaluations	All safety evaluations will be done by the study physician [name], a Developmental-Behavioral Pediatrician at the Children's Hospital of Philadelphia. The Safety Monitoring Uniform Report Form (SMURF) will be used to assess STX209 specific side effects. In addition, safety and tolerability of STX209 will be determined by Adverse Events (AE), Vital Signs (heart rate and blood pressure), and a blood draw for BUN and creatinine labs. [name] or one of her attendings will be on call for any problems that might arise in between study visits. Families will be advised to call 911 in case of an emergency when they are not at our Center.
Statistical And Analytic Plan	Primary statistical analyses assess baseline versus post acute-dose (placebo, STX209 15 and 30 mg) changes for (1) M100 auditory latency, and (2) post-stimulus auditory gamma-band activity. For each dependent measure, ANOVAs with dose as a repeated measure will examine baseline versus post acute-dose changes (analyses showing no significant differences across time in baseline M100 and gamma measures will allow

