Although this study did not show statistically significant effects of STX209 on irritability symptoms, subjects showed evidence of global behavioral improvement. Subjects' most troublesome behaviors as judged by the parents/caregivers/legally authorized representatives (LARs) were rated on a Visual Analog Scale (VAS) as more improved when the subjects were on STX209 compared to placebo ($p < 0.05$). In the Per Protocol (PP) study population, more clinicians and parent/caregivers rated the subjects' behavior as preferable on STX209 versus placebo by a 2:1 ratio. A post-hoc analysis showed that subjects with higher baseline scores on the Lethargy/Social Withdrawal scale of the ABC-C showed significantly greater improvement on that scale when treated with STX209, as well as on the Vineland Adaptive Behavior Scales-II (VABS-II) Socialization domain ($p < 0.050$ for both comparisons). These subjects also showed significantly greater improvement on multiple measures of global improvement, including the CGI-I, CGI-S, and blinded treatment preference ratings by the clinicians and by parent/caregivers ($p \leq 0.010$ for all comparisons) (22001 Clinical Study Report). No significant safety or tolerability concerns were apparent in Study 22001. Overall, 58 (92.1%) of 63 subjects reported AEs; the percentage was the same (45 subjects, 71.4%) during treatment with STX209 and placebo. AEs with incidence $> 5\%$ and greater than twice the incidence in placebo included headache, sedation (both 8% on STX209 versus 2% on placebo), fatigue, and vomiting (both 6% on STX209 versus 2% on placebo).

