The proportion of subjects with AEs deemed to be at least possibly related to study drug was higher with STX209 (53.9%) than with placebo (46.0%). The most commonly reported treatment-related AEs in STX209-treated subjects were sedation (7.9%), irritability (6.3%), increased appetite (6.3%), headache (6.3%), aggression (4.8%), anxiety (4.8%), and fatigue (4.8%). The majority of AEs were mild or moderate in severity, and most resolved spontaneously. Five subjects reported severe AEs (two subjects with increased irritability and one each with aggression, diarrhea, and dental caries requiring extraction). One subject who was tapering from STX209 treatment experienced an SAE of worsened irritability that resulted in hospitalization and study withdrawal. This subject had a prior history of similar events requiring multiple hospitalizations. The Investigator assessed the event as severe in intensity and possibly related to study drug taper. Two subjects discontinued while on placebo, both for worsened irritability during tapering of study medication. No deaths or other significant AEs were reported.

The following data were reported from Seaside Therapeutics Study 22003, a Phase 2 open-label, flexible-dose evaluation of the safety and tolerability of STX209 for treatment of irritability in subjects with autism spectrum disorders. This open-label study employed a flexible-dose schedule to define the optimal tolerability dose (OTD) for each subject. The OTD was defined as either the dose that achieved a behavior rating of very much improved on the CGI-I or as the maximum tolerated dose. Dosing decisions were based on the average response since the last dose change compared to baseline behavior. The starting dose of 1 mg BID could be increased every three days to 2 mg BID, 3 mg BID, 5 mg BID and then 10 mg BID. The dose for subjects who were at least 12 years of age could have been increased to 10 mg TID. After the 8-week assessment, subjects were tapered from study drug during a 2-week titrated withdrawal period.

Efficacy endpoints included the ABC-C, CGI-S, CGI-I, CYBOCS-PDD, VABS-II, CASI-Anx, VAS-Target Behavior, SRS, ADHD-IV, and Leiter-R Brief IQ. Safety evaluations included AEs, laboratory assessments, vital signs, ECG, and physical examination.

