4.2 Screening Visit

On the screening visit participants will be given Informed Consent and the following assessments and procedures will be administered to confirm eligibility and safety. Measures bearing on exclusion and inclusion criteria will be done first, and if determined eligible to participate, participants will complete the other measures.

- Neuropsychological evaluation, including both clinical and behavioral testing (*only if applicable*)
- Physical Examination (*include abdominal palpation to assess for liver enlargement, assessing for decreased tone and postural problems, increased drooling and poor orofacial tone, problems holding head up, and difficulty with coordination of motor actions*), *Height and Weight, and Medical/Surgical History Review*
- Vital Signs: *Temperature, Blood Pressure, Heart Rate, and Respiratory Rate*
- Blood Draw (*BUN and Creatinine*) (To minimize harm to the subject, in cases where subject is unable to do a blood draw on the day of the screening visit due to anxiety/fear/discomfort, if no medical risk factors are identified during medical history review, we will either accept BUN and Creatinine results from an outside source within 3 months of the first imaging visit or attempt to do the blood draw on the day of the imaging visit.)

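### The safety analysis takes in everyone entered at screening and names no breakdown by placebo, 15 mg and 30 mg, so as written it does not show adverse events on STX209 against placebo

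*Combined protocol and SAP*

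**What the plan says.** Section 5.5 makes safety a secondary endpoint: "Safety and tolerability of STX209 based on Adverse Events". Its planned analysis is the three sentences of Section 5.6.4. The first sets the population: "All subjects entered into the study at screening visit will be included in the safety analysis". The second lists the summary factors: "The frequencies of AEs by type, body system, severity and relationship to study drug will be summarized". The third says that any SAEs will be described in detail.

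No other section adds a breakdown by condition. Sections 5.6 and 5.6.2 name dose as a repeated measure for the MEG measures, and the remark on secondary endpoints in 5.6.2 covers only MRS-MEG correlations. Under Section 6.1.3 each subject receives all three conditions.

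On entry, Section 4.2 says: "Measures bearing on exclusion and inclusion criteria will be done first, and if determined eligible to participate, participants will complete the other measures". So eligibility is still being settled at that visit, and Section 5.3 excludes subjects whose renal tests there are abnormal. Section 7.2 defines an AE as occurring in someone who has received an intervention.

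On vital signs, the Safety Evaluations row of the Protocol Synopsis states that "safety and tolerability of STX209 will be determined by Adverse Events (AE), Vital Signs (heart rate and blood pressure") and a blood draw. Section 5.6.4 mentions no vital-sign summary.

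**The concern.** In a crossover where everyone takes placebo and both doses, an AE table without condition mixes drug and placebo experience in the same people. It cannot be read for a drug effect, whichever way the effect goes. The breakdown by relationship to study drug does not repair this, because it is a judgement on each event and not a comparison with control.

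The population adds a smaller problem. Someone entered at screening and never dosed can count in the denominator but, by the definition in 7.2, not in the numerator.

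By-condition tolerability is useful here: 30 mg in one dose is twice the largest single dose in the earlier patient trials that Section 1.3.1.1 describes (15 mg three times daily; 30/15 = 2).

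**Working it through.** Section 5.6.4 gives no figure to reproduce. The check is what its output could show.

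**1. What an undivided figure hides.** For the earlier placebo-controlled crossover, Section 1.3.1.1 reports: "Overall, 58 (92.1%) of 63 subjects reported AEs; the percentage was the same (45 subjects, 71.4%) during treatment with STX209 and placebo". That is 58/63 = 92.1% overall and 45/63 = 71.4% on each treatment. Only the split shows that the overall rates were equal, and only the split shows headache and sedation at 8% on STX209 against 2% on placebo.

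**2. Causality rating as a substitute.** In the same trial 46.0% of subjects on placebo, and 53.9% on STX209, had AEs rated at least possibly related. A rating given to 46.0% of subjects on placebo does not isolate drug effects.

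**3. Illustration for this design.** Assumptions: the 2% and 8% above, which come from 4-week treatment, are used as single-visit rates; visits are independent; n = 36 (Section 5.7).
- Drug effect (2%, 8%, 8%): 1 − 0.98 × 0.92 × 0.92 = 17.1% ever affected, or 36 × 0.1705 = 6.1 subjects.
- No drug effect, 6% at each visit: 1 − 0.94³ = 16.9%, or 36 × 0.1694 = 6.1 subjects.
- Split by condition, expected counts are 0.7, 2.9 and 2.9 in the first case (36 × 0.02, 36 × 0.08, 36 × 0.08) and 2.2 each in the second (36 × 0.06).

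The 6% is the mean of 2%, 8% and 8%, so the near match is built in. It shows that an undivided frequency cannot tell the two cases apart; it does not forecast rates.

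**4. What the split can and cannot deliver.** On these rates, the expected number of subjects with the event under exactly one of placebo and one dose is 36 × (0.98 × 0.08 + 0.02 × 0.92) = 36 × 0.0968 = 3.5. A two-sided exact McNemar test at 0.05 needs at least 6 such subjects (2 × 0.5⁵ = 0.063; 2 × 0.5⁶ = 0.031), and its power here is about 3%. Exact 95% intervals are 0.1% to 14.5% for 1/36 and 1.8% to 22.5% for 3/36. The table is descriptive only.

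**5. Denominator.** Planned rate = rate among dosed × (N − u)/N, with u the number never dosed. The documents do not give u. Purely as an assumed range with N = 40 and 8 subjects with an AE, the planned rate is 8/40 = 20.0% throughout. Among dosed subjects it is 20.0% (u = 0), 8/36 = 22.2% (u = 4) or 8/30 = 26.7% (u = 10).

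**6. Assigning AEs to a dose.** Visits are at least 4 days apart (Section 4.3) and the half-life is 5.85 hours (Section 1.3.1.2): 96/5.85 = 16.4 half-lives. Assigning an AE to the last dose given is therefore reasonable.
- On the sequence in 3.1.3, the end-of-visit SMURF falls about 60 + (30 to 45) + 60 = 150 to 165 minutes after dosing, taking MEG durations from 5.1.6 and 5.2.1. That is under half of one half-life (2.75/5.85 = 0.47), so a same-visit window alone would miss later effects.
- Later onsets are not caught equally. At the next visit the SMURF asks about the interval since the last one (5.1.3), but no routine visit follows Visit 3. In the three orders of Section 3.2, Visit 3 is 30 mg in two, placebo in one and 15 mg in none.

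Same-visit and later onsets should therefore both be shown, and kept apart.

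**The case against.** **The section never says AEs will be pooled.** This stands. A reader might infer a decision to pool, but 5.6.4 is silent on condition. The supportable statement is that its factor list omits condition and nothing elsewhere supplies it.

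**The endpoint names no placebo contrast, and the table can be made at any time.** Section 5.5 names only AEs, and the comparative objectives in 2.1 concern MEG and MRS. Onset times (7.2), the pharmacist's assignment (3.2) and unblinding at study close (6.1.3) would allow a split later. So no data are lost. But the trial includes placebo, and leaving the split to later leaves its denominator and attribution rule open.

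**Few subjects will be entered and never dosed.** Section 3.1.1 screens eligibility by telephone first, so this may be right. A reader might take 40 minus 38 (3.3.2), or the 4 losses in 5.7, as the number never dosed and derive a 5% or 10% dilution. The documents do not support that: these are non-evaluable subjects and lost or incomplete data sets, and such subjects may well have been dosed.

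**Vital signs are handled.** Largely so. Section 7 already calls for vital signs before and after MEG, 5.3 acts on significant blood-pressure changes, and such changes can be recorded as AEs. A reader might infer that hypotension goes unmonitored; it does not. Only a summary by condition is missing. The absence of the post-dose reading from 4.3 and the 5.2.1 timetables is a schedule inconsistency. The documents give no blood-pressure SD, so the precision of such a summary cannot be derived from them.

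**The split will have little precision.** True, as step 4 shows. That argues against testing, not against showing the counts.

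**Conclusion.** The point holds as a modest reporting correction. Section 5.6.4 sets a population that need not have been dosed and a list of factors without condition. Output built to that text would not show AEs on 15 mg or 30 mg against placebo, and any undosed subjects would lower the rates by an unknown amount.

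The illustration (17.1% against 16.9%) rests on borrowed 4-week rates, independent visits and a no-effect rate chosen to match. The argument does not depend on its size, since the 92.1% and 71.4% from the earlier crossover make the same point with real data.

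The documents do not support reading this as a threat to the study's main results, or as a promise that the split would establish a dose difference in tolerability. This is an exploratory MEG study, and the primary conclusions are unaffected.

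**What to change.** In Section 5.6.4:
- **(a)** Define the safety set as subjects who received at least one dose of study drug or placebo. List screening-only subjects separately.
- **(b)** Tabulate AE frequencies descriptively for placebo, 15 mg and 30 mg, with subjects dosed under that condition as denominator. Assign each AE to the last dose given. Show same-visit and later onsets separately, and note that follow-up after Visit 3 is not routine.
- **(c)** Optionally, add a descriptive summary by condition of the blood pressure and heart rate that Section 7 already calls for before and after MEG, and make 4.3 and the 5.2.1 timetables list the post-dose reading.

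The cost is a few lines of text and one or two extra descriptive tables. Parts (a) and (b) need no new data, and (c) needs none if the Section 7 readings are taken. The tables will hold small counts with little precision for comparing conditions, so they should carry no tests.
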